## 4. PARTICIPANT ENTRY

A poster will be used in the waiting area and staff room of the Audiology department at Charing Cross Hospital. This poster will also be used on social media.

### 4.1 CONSENT

Consent to enter the study must be sought from each participant only after a full explanation has been given, an information leaflet offered and time allowed for consideration. Signed participant consent should be obtained. Participants will be provided the consent form and information sheet via email or directly (meeting organised over the phone – Audiology department at Charing Cross Hospital). They will be given a minimum of 24 hours and maximum of 7 days to contact the researcher to go ahead with the study and a date will be organised to sign the consent form and begin screening. In this time, participants can also ask any questions they may have to the researcher via email or phone. The right of the participant to refuse to participate without giving reasons must be respected. All participants are free to withdraw at any time from the protocol treatment without giving reasons and without prejudicing further treatment.

### 4.3 INCLUSION CRITERIA

- 18-35 years old (as age can affect cochlea hair cell function)
- Healthy participants with no significant medical conditions
- 0.25 Hz to 8 kHz PTA in both ears have thresholds  $\leq$  20 dB HL indicating normal hearing
- Otoscopy to ensure no otological abnormalities
- No exposure to abnormally loud sounds in the past 24 hours
- Full capacity to consent

- Able to speak fluent English so information sheets, consent forms and instructions are fully understood
- Previous intention to attend a loud noise event during the course of the study, without the use of hearing protection

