## **3. STUDY DESIGN**

Type of Study: Basic Science Study, Between Groups Trial

Aim: To investigate if previous sound conditioning reduces susceptibility to TTS and tinnitus when comparing to those without prior exposure.

Purpose: To increase our understanding on the effects of noise exposure.

Duration: Data collection will be completed by February 2020

Participants: 40 normal hearing young (18-35) participants in good general health and fluent in English.

Spilt into groups of two. One group (20, 10f:10m) with previous exposure i.e. nightclubs ++, the other group (20, 10f:10m) with less exposure measured through NESI.

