### **3.2 METHODS**

Screening - Participants will be asked about the health of their ears and ears will be examined to ensure there are no abnormalities (Otoscopy). A hearing test (PTA) will then be performed; This test will involve participants listening to a series of tones at different pitches and volumes through headphones and participants will press a button whenever they hear a tone. The researcher will also undertake a structured interview to assess noise exposure history (NESI) and the results from the screen will see if you are eligible to participate in this research. With participants consent, if any abnormalities are detected at any point, your GP will be informed with a copy of the results. Participants will subsequently be excluded from the study and information destroyed. Example of NESI question: I'd like you to estimate how noisy it was when you [engaged in the activity] by answering this question: If you and I were 4 feet apart in that situation, which of the following would you need to do to communicate with me? [The interviewer presents the six options from the Speech Communication Table.]

Each session will require 35 minutes (35 x 3 = 105 minutes overall).

SESSION ONE - Prior to noise exposure (continued same day after screening passed if eligible):

Test battery - High frequency audiometry, Distortion Product Otoacoustic Emissions, Middle Ear Muscle Reflex, Speech in Noise test, Tinnitus Functional Index (Around 35 minute testing time with breaks if required)

- Extended Frequency Pure Tone Audiometry (~ 8 minutes)

Similar to Screening, participants will be asked to press the button when they hear a sound through the headphones in a sound proof booth.

- Distortion Product Otoacoustic Emissions (~ 5 minutes)

A small tip will be placed in participants' ear and they will hear a sound. The tip measures a response from hair cells in the cochlea and they will not need to do anything.

- Middle Ear Muscle Reflex (~ 8 minutes)

A small tip will be placed in both ears and again a sound heard however this sound will gradually get louder until an involuntary muscle reflex is noted.

- Speech in Noise Test (~ 5 minutes)  
Participants will be asked to repeat back a list of words as best as they can.
- Tinnitus Functional Index (~ 8 minutes)  
Participants will be given a self-report sheet in which they have to fill out aspects of any tinnitus experienced.

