SESSION TWO - Exposure at single loud music event (Important that this is part of participants' normal recreational routine, and specifically require that attendance is not prompted by participation in this study): Participants to use sound level meter provided from the Audiology Department at Charing Cross Hospital to measure sound levels inside the loud event.

Morning after exposure: Repeat test battery from session one - Ideally as soon as event is over.

SESSION THREE: 1 week later (recovery): Repeat test battery.

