## 6. ASSESSMENT AND FOLLOW-UP

Participants will receive a week post-exposure test battery to assess recovery. After this, there will be no follow up in the Audiology Department. If abnormal results are highlighted at any stage, participants will be excluded from the study and as consented, a letter containing the results will be sent to the GP. Participants will subsequently be excluded from the study and information destroyed.

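### The only quiet period before the single pre-event test is 24 hours, and time since last loud exposure is not recorded, so leftover threshold shift could differ by group and mimic protection

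*Combined protocol and SAP*

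**What the plan says.** - **Quiet period.** Section 4.3 (Inclusion Criteria) requires "No exposure to abnormally loud sounds in the past 24 hours". The level that counts as abnormally loud is not defined.
- **Baseline.** In section 3.2 (Methods), session one is "continued same day after screening passed if eligible". No pre-event test is repeated.
- **Post-event test.** "Morning after exposure: Repeat test battery from session one - Ideally as soon as event is over" (section 3.2).
- **Recovery test.** "SESSION THREE: 1 week later (recovery): Repeat test battery" (section 3.2). Section 6 repeats it: "Participants will receive a week post-exposure test battery to assess recovery".
- **Groups.** "One group (20, 10f:10m) with previous exposure i.e. nightclubs ++, the other group (20, 10f:10m) with less exposure measured through NESI" (section 3).
- **Aim.** Sections 3 and the Study Summary ask whether earlier sound conditioning lowers susceptibility to TTS and tinnitus.
- **Analysis.** Section 7 says who will analyse the data and how long they are kept. It gives no method, change score or adjustment.

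No section sets a longer quiet period, records the time since the last loud exposure, or adjusts for it.

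**The concern.** TTS is naturally read as the post-event threshold minus the session-one threshold. If an ear has not fully recovered from an earlier exposure at session one, the reference is raised and the measured shift is smaller than the true one. The other measures that use session one as reference (DPOAE, MEMR, speech in noise) are open to the same problem.

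This would be extra noise if it affected both groups alike. It may not, because one group is selected for nightclub exposure and the other for less exposure. Someone who left a club at 03:00 on Sunday could be tested at 09:00 on Monday, 30 hours later, and meet the criterion. A participant with little exposure will less often be in that position.

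The error would then favour the hypothesis: less measured TTS in the conditioned group without any conditioning. It could also flatter recovery at one week, since a return to a raised reference looks complete. If the timing is not recorded when each session takes place, it cannot be reliably recovered afterwards.

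**Working it through.** The plan has no figure to reproduce. It states 40 participants without a derivation and gives no effect size, standard deviation (SD) or recovery rate. Everything below beyond the two intervals, the group size and the group definitions is an assumption.

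**1. Intervals.** One week is 7 × 24 = 168 h. Against the 24 h entry window the ratio is 168/24 = 7.

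**2. Bias in one participant.** Let T be the true shift from the study event, r the leftover shift at session one, and r′ what remains of that leftover at the study event. If shifts add, measured TTS = T − (r − r′). The bias is the full r only if the leftover has gone by the event. It is zero if r′ = r.

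**3. How often baseline falls soon after a loud event.** Assume events every L hours and session one at a random time once 24 h have passed. The share tested 24–72 h after an event is 48/(L − 24):
- twice weekly (L = 84): 48/60 = 80%
- weekly (L = 168): 48/144 = 33.3%
- four-weekly (L = 672): 48/648 = 7.4%

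**4. Bias in the group contrast.** Assume a mean residual of 2–5 dB at 24–72 h, none later, and r′ = 0. Bias = difference in shares × residual:
- weekly v four-weekly: 0.259 × 2 to 5 dB = 0.5 to 1.3 dB
- twice-weekly v four-weekly: 0.726 × 2 to 5 dB = 1.5 to 3.6 dB

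**5. Is a 2–5 dB residual plausible?** Under exponential recovery with half-life h, the share left at time t is 0.5^(t/h). The mean over 24–72 h is h × (0.5^(24/h) − 0.5^(72/h)) / (48 ln 2).

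| Assumed half-life | Left at 24 h | Mean over 24–72 h | Left at 168 h | Initial shift needed for a 2–5 dB mean |
|---|---|---|---|---|
| 4 h | 2% | 0.2% | 0% | not attainable |
| 12 h | 25% | 8.5% | 0.006% | 24–59 dB |
| 24 h | 50% | 27% | 0.8% | 7–18 dB |
| 48 h | 71% | 51% | 8.8% | 4–10 dB |

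The residual in step 4 therefore needs slow recovery or large initial shifts. With fast recovery the bias is close to zero.

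**6. Effect of r′.** Suppose a twice-weekly attender's next outing, at 84 h, is the study event. The share of the initial shift still present is then 8.8% (24 h half-life) or 29.7% (48 h). Against the 24–72 h means, 8.8/27.1 = 33% and 29.7/51.0 = 58% of the bias cancels. The cancellation is largest where recovery is slow, which is also where the residual is largest.

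**7. Consequence for the test.** With 20 per group, no true effect and two-sided alpha 0.05, the chance of a false protective result is Φ(bias/SE − 1.96), where SE = SD × √(2/20). The nominal rate in that direction is 2.5%.

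| Mean bias | SD 4 dB | SD 6 dB | SD 8 dB |
|---|---|---|---|
| 0.5 dB (a quarter of the exposed group carry 2 dB) | 6% | 4.5% | 4% |
| 1 dB (half carry 2 dB) | 12% | 8% | 6% |
| 2 dB (half carry 4 dB) | 35% | 18% | 12% |

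**The case against.** **The one-week test is not a recovery time.** A reader might infer that the study itself holds that ears need a week to recover. The documents do not say so: sections 3.2 and 6 schedule a check at one week and give no recovery rate. This objection stands. The seven-fold difference shows an unexplained inconsistency and does not prove that shift remains at 24 hours.

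**The sizes are assumed.** The 2–5 dB residual has no source in the documents. Section 3 defines the groups by exposure history and gives no current attendance frequency. Both groups must already intend to attend a loud event (section 4.3), as part of their normal routine (section 3.2). This also stands. More recent exposure in the nightclub group is plausible, but its extent is unknown.

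**Other safeguards.** The 20 dB HL limit in sections 4.3 and 4.4 does not close the gap. It is an absolute limit, so a small shift can pass, and it stops at 8 kHz while an outcome is extended high-frequency audiometry. Session three could reveal carry-over if thresholds came out better than at session one, but no such check is planned and no quiet period is required before session three.

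**Stronger remedies.** A reader might conclude that the entry window should simply be set to seven days. In the model above every weekly attender has been exposed within seven days. Such a rule would exclude them or make them break the routine under study, and an exemption for them would apply the rule unequally by group. Using the better of the session-one and session-three thresholds as reference is no clean answer either: the minimum of two noisy measurements inflates TTS, and session three is itself unprotected.

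**Conclusion.** The point holds as a possible, unquantified bias in the main group contrast. The 24-hour criterion alone protects the only pre-event reference, likely recency of exposure differs by group definition, and nothing planned would detect or adjust for it. The direction favours the hypothesis wherever leftover shift at baseline has faded by the study event.

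The size runs from near zero (fast recovery, or equal leftover shift at the event) to about 1 dB for weekly against four-weekly attenders, given an assumed 2–5 dB residual. It is larger for more frequent attenders, before allowing for shift still present at the event. The statement that frequent clubbers' TTS will look falsely small goes further than the documents allow; they support only that it can. This should be fixed, because the cost is low and the missing information cannot be reliably obtained after data collection. The evidence does not show that the contrast is invalid as planned.

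**What to change.** 1. Record hours since last loud exposure for every participant at session one, before the study event and at session three, with a stated definition of loud. This is one added question, which at session one can sit beside the NESI interview.
2. Book session one as long after the last loud exposure as practical, using the same rule in both groups.
3. In section 7, plan a sensitivity analysis of the group contrast that either adjusts for time since last loud exposure or restricts to participants with a longer quiet interval. Fix the choice and any cut-off before the data are seen. State that wording about protection will be qualified if the contrast does not hold.
4. Justify the 24-hour window in section 4.3, or reconcile it with the one-week recovery check in sections 3.2 and 6.

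The cost is one more question and slightly less flexible booking. The sensitivity analysis will lose some precision because recency is correlated with group, and with 20 per group a restricted analysis may be small.

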## **2. STUDY OBJECTIVES**

- i) To identify if there is a relationship between previous sound exposure levels and TTS and tinnitus after a single loud noise event.

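### Hearing protection actually worn and other loud exposure between sessions are not recorded, and either could differ between the two noise-habit groups

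*Combined protocol and SAP*

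**What the plan says.** The objective in section 2 is "To identify if there is a relationship between previous sound exposure levels and TTS and tinnitus after a single loud noise event". It therefore depends on one event as the exposure.

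Going without protection appears once, as an inclusion criterion in section 4.3: "Previous intention to attend a loud noise event during the course of the study, without the use of hearing protection". The same section has the only rule on other loud sound: "No exposure to abnormally loud sounds in the past 24 hours". Both apply at entry.

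At the event, section 3.2 has "Participants to use sound level meter provided from the Audiology Department", and the purpose given is "to measure sound levels inside the loud event". The later visits are described as "Morning after exposure: Repeat test battery from session one" and "SESSION THREE: 1 week later (recovery): Repeat test battery". The battery has five parts: extended-frequency audiometry, otoacoustic emissions, middle ear muscle reflex, speech in noise and the tinnitus questionnaire. The noise history interview (NESI) is held at screening, before the event.

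Section 3 forms two groups of 20 by past noise exposure, one with frequent nightclub-type exposure and one with less. Sections 4.5, 6 and 7 (withdrawal, follow-up, statistics) have no rule for participants who wore protection or were exposed again.

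**The concern.** The comparison of TTS between groups is interpretable only if the dose at the ear is comparable, or is known well enough to allow for. A venue reading gives the same number whether or not earplugs were worn, and it cannot reveal a second event on another day. No part of the battery asks about either.

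The groups are built on noise habits and are not randomised, so there is no design reason to expect protection use or further outings to balance. Two errors are possible:

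- **Protection at the event (session two).** If the high-exposure group departs more often from its stated intention, its mean TTS falls and the result resembles conditioning. If the low-exposure group does so, a real conditioning effect is hidden.
- **Loud exposure in the following week (session three).** If the high-exposure group goes out again more often, fresh threshold shift is read as poor recovery.

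Loud exposure between session one and the event is also unrecorded. The 24-hour entry rule shows that the authors regard recent loud sound as a contaminant, but the plan carries no equivalent question forward to the later visits. These facts cannot be reliably recovered if they are not captured at the visit.

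**Working it through.** **What each element can detect**

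| Element | Timing | Shows protection worn? | Shows other loud exposure? |
|---|---|---|---|
| Intention to go unprotected (4.3) | Entry | No, intention only | No |
| 24-hour loud-sound rule (4.3) | Entry | No | Only before entry |
| NESI (3.2) | Screening | Not at the event | Past history only |
| Sound level meter (3.2) | Event | No, venue level | No |
| Test battery (3.2) | Sessions two and three | No | No |

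No row fills the gap for the event itself or for the intervals between sessions.

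**Illustrative size for the protection half.** The plan states no alpha, SD, effect size or power, so there is no figure of its own to reproduce.

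Input from the plan: 20 per group (section 3).

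Inputs assumed: protection lowers mean TTS by 3-5 dB; its use differs by 10-30 percentage points between groups; TTS SD 5 dB; two-sided alpha 0.05; true group difference zero; normal approximation.

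1. Spurious difference = difference in use × reduction in TTS.
   - Low end: 0.10 × 3 = 0.3 dB.
   - High end: 0.30 × 5 = 1.5 dB.
2. In SD units: 0.3/5 = 0.06 and 1.5/5 = 0.30.
3. Standard error of the group difference in SD units: √(2/20) = 0.316.
4. False-positive rate = [1 − Φ(1.960 − b/0.316)] + Φ(−1.960 − b/0.316), where b is the spurious difference in SD units.
   - b = 0.06: b/0.316 = 0.190; 0.038 + 0.016 = 0.054.
   - b = 0.30: b/0.316 = 0.949; 0.156 + 0.002 = 0.158.

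The nominal 5% becomes about 5.4% at the low end and about 16% at the high end. If use is equal in the two groups, the difference in use is zero and so is the bias when there is no true difference.

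**Re-exposure half.** The documents offer nothing from which to size it, and no figure is put on it here. It bears mainly on the one-week recovery comparison.

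**The case against.** The strongest reply is that the entry criterion already does much of the work. It admits only people who mean to go unprotected, to an event within their normal routine, and it applies equally to both groups. Habitual protection users should be screened out, and bias then needs departures from intention at different rates by group. This stands, and it limits how large a difference is credible. It does not show what people actually did.

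A reader might infer that protection use does differ by group. The documents do not support that: they give no rates, and nothing says experienced attenders protect themselves more. The group definition lends some support to more re-exposure in the high-exposure group, but not to more protection.

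A reader might also infer that protected or re-exposed participants will be counted as having had one unprotected exposure. Section 7 does not say so. It names no analysis set, model or covariate for any purpose, so that reading comes only from silence. The protocol is also brief, and a data-collection form outside these documents might hold such a question.

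Larger sizes can be produced: 50% against 10% protected with a reduction of 1.0 SD gives 0.40 SD and 24.4% false positives. A 40-point gap is hard to reconcile with the entry criterion, so that figure should not set the severity.

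Two further points stand. Re-exposure that worsened the high-exposure group's recovery would work against the conditioning hypothesis, so the two errors need not add up. And a 24-hour rule could not be repeated at session two, which falls the morning after the event; what is needed there is a question about other exposure.

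**Conclusion.** The gap in recording is real: as written, the plan collects neither protection worn at the event nor loud exposure between sessions. The bias is possible, not established. It requires the behaviour to differ by group, and its direction depends on which behaviour and which group.

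The range of 0.3-1.5 dB rests wholly on the assumed TTS reduction, difference in use and SD. Its upper end is just under one standard error of the comparison (0.30 against 0.316 SD). That is enough to colour a positive finding but not enough to invalidate the study.

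It does not follow that the main analysis should be confined to unprotected participants. That would select on behaviour after entry, and people prone to tinnitus or threshold shift may be the ones who protect themselves. This is a cheap improvement, worth making because the information is easily lost and costs little to collect.

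**What to change.** **Session two:** record whether protection was worn for none, part or all of the event, and any other loud exposure since session one.

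**Session three:** record any loud exposure since the event.

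**Section 7:** keep all participants in the main analysis. Pre-specify two sensitivity analyses:

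- the TTS comparison restricted to participants who wore no protection and had no other recent loud exposure, with *recent* defined in advance;
- the recovery comparison restricted to participants not re-exposed before session three.

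Report the recorded frequencies by group, so that a reader can see whether the behaviours differed.

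**Cost:** about one minute per visit and some extra analysis. The questions do not prompt attendance or alter what participants do. The restricted groups will be smaller and possibly selected: a 30-point difference in use means at least 0.30 × 20 = 6 participants leave one group, leaving 14 at most, and the planned 10:10 sex balance may be lost. The restricted results should therefore be read as checks on the main result.

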#### **4.4 EXCLUSION CRITERIA**

- No permanent tinnitus or hyperacusis (sensitivity to loud sounds) which would mean participants are unable to undertake all testing and a high exposure event
- Any contraindications for testing i.e. excessive wax, infections
- One or more frequencies 0.25 Hz to 8 kHz > 20 dB HL in either ear
- Not involved in current research or have recently been involved in any research prior to recruitment

#### **4.5 WITHDRAWAL CRITERIA**

A consent form will be obtained prior to commencing the study however participants' may withdraw at any time by notifying the researcher in person or in written form and without providing any reason.

